4. A common reduced function variant of ABCG2, Q141K, paradoxically leads to reduced response to ALLO. The ABCG2 locus identified in our GWAS included the nonsynonymous variant, Q141K (rs2231142), which is known to have reduced transport function due to reduced protein expression^{23,24}. This variant had the lowest p-value of all ABCG2 nonsynonymous variants that were either genotyped or imputed. Interestingly, Q141K has also been associated, at genomewide level significance, with response to rosuvastatin¹⁹. Because our preliminary studies indicate that ABCG2 is an efflux transporter for OXY and ALLO, we expected that the variant allele would be associated with higher drug levels through increased absorption and reduced renal secretion mechanisms resulting in higher drug levels and improved response. The fact that we found that the variant was associated with a worse response suggests another mechanism. We propose that Q141K results in lower drug levels in the renal tubule, consistent with reduced renal secretion of the drugs. The lower levels of OXY in the renal tubule result in reduced inhibition of UA reabsorptive transporters through competitive inhibition mechanisms. In support of our hypothesis, we recently found that OXY and ALLO inhibit UA uptake via URAT1. Our data are consistent with previous studies showing that OXY is a substrate of URAT1²⁵. Also, reviewing data in the older literature we noted that ALLO treatment was associated with an increased renal clearance of UA in many patients after initiation of ALLO treatment²⁶, supporting our hypothesis that ALLO and/or OXY inhibit UA reabsorptive transporters. Therefore we propose that ABCG2-mediated secretion of OXY results in sufficiently high levels of the drug in the renal tubule to competitively inhibit uric acid reabsorptive transporters, e.g., URAT1. Competitive inhibition of uric acid reabsorption leads to increased UA excretion and therefore reduced serum levels of UA. Notably, ABCG2 can concentrate its substrates >20-fold^{20,27} and maximum plasma unbound concentrations of OXY and ALLO are as high as 100 μM . Therefore, estimated proximal tubule concentrations of OXY and ALLO could be in the mM range²⁸. In contrast, lower tubule levels of OXY, which are achieved in individuals with the Q141K variant, result in less inhibition of UA reabsorption and therefore, poorer response. If our hypotheses are proven, our studies will lead to a new understanding of the mechanisms of action of ALLO and its active metabolite OXY.

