
5. There is a major gap in our understanding of the genetic factors that determine response to OXY in all ethnic groups including under-represented populations. In contrast to the multiple GWAS studies identifying genetic risk factors for hyperuricemia and gout, there has been no published GWAS related to ALLO response. In preliminary studies using samples from individuals of European ancestry, we conducted the first GWAS of response to ALLO. We attempt to fill this gap by evaluating the effects of ABCG2 gene variants on the pharmacodynamics and pharmacokinetics of ALLO. This effort is a mechanistic genotype to phenotype pharmacogenetic study designed to supplement ongoing investigations of the contribution of genetic variability in drug

transporters to inter-individual variation in drug response. Comparing the variability in uric acid levels and renal clearance of ALLO in individuals with different ABCG2 genotypes will provide information about the extent to which genetic factors contribute to inter-individual differences in the renal elimination and response to ALLO. Investigating these polymorphic variants, which occur at relatively high frequencies within Asians and Europeans, will provide vital information for the purpose of guiding antihyperuricemic drug regimens in these populations.

NUMBER OF SUBJECTS: 15 subjects will participate in the study. 5 from each genotype: homozygous recessive, homozygous dominant, heterozygous. This number has been selected so that our study will be 80% powered to detect a 40% change in allopurinol clearance.

GENDER OF SUBJECTS: Both males and females will be enrolled for this study. Because allopurinol has been shown to have detrimental effects on unborn fetuses, pregnant women will not be allowed to participate in the study.

AGE OF SUBJECTS: Healthy volunteers over 18 years of age will be enrolled

RACIAL AND ETHNIC ORIGIN: Subjects of Asian and European descent will be enrolled in this study. These ethnicities are known to carry the genetic variant of interest for this study.

INCLUSION CRITERIA:

1. Subject self-identify racial background; identify themselves, their parents, and their 4 grandparents as European or Asian;
2. Subjects are generally healthy with approved (normal) laboratory values for:
 - CBC Panel: WBC, RBC, Hemoglobin, Hematocrit, MCV, MCH, MCHC, RDW, Platelet Count, MPV and Differential (Absolute and Percent - Neutrophils, Lymphocytes, Monocytes, Eosinophils, and Basophils)

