mechanism of secretory clearance and consequent longitudinal changes in OXY secretory CL and influence of pharmacogenomics (ABCG2) and demographic covariates (creatinine clearance, age, gender, race and body weight) on secretory and renal CL. By use of the physiological model, we will also attempt to estimate the drug concentration in the renal tubule; by knowing plasma and urinary concentration of OXY, and by estimating filtration and secretory clearance of OXY, we will be able to estimate the time profile of tubular concentrations of OXY. These tubular OXY concentrations represent concentration at the proposed site of action and they will further be linked with the pharmacodynamic response. A model describing concentration dependent inhibition of UA re-absorption from the renal tubule by OXY will be implemented. We will examine linear and non-linear (Emax type of model) relationships between tubular OXY and inhibition of UA reabsorption. In the pharmacokinetic modeling, we expect to see a significant influence of creatinine clearance on renal clearance and a significant influence of ABCG2 genotype on secretory CL and oral bioavailability, as described below. In the pharmacokinetic-pharmacodynamic analysis we expect that individuals with higher tubular concentrations of OXY will show the better response in terms of plasma UA lowering resulting in higher urine UA concentrations. Consequently, higher tubular concentrations will be mostly expected in individuals with high secretory clearance, e.g. individuals with ABCG2 141Q/Q, however the modeling may also account for other factors contributing to high tubular concentration, such as higher filtration rates and other factors, therefore providing more granularity and better mechanistic understanding in all processes leading to overall UA physiology. Although this specific PKPD analysis will be focused on the mechanism and role of ABCG2 in UA response to ALLO and OXY, the established mechanistic framework can be used to test the role of potential new pharmacogenetic variants. Longitudinal PKPD modeling using nonlinear mixed effects is a method carrying the most power to separate the signal from the noise; therefore modeling analysis will be associated with at least 80% power to detect differences in primary endpoints (net secretory clearance and change in UA) as described above. In addition to confirming the result of the primary analysis, this analysis will establish a mechanistic representation of the physiology underlying UA metabolism, therefore providing strong support and evidence to our mechanistic hypothesis. Pharmacokinetic parameters including renal clearance, and net reabsorptive or secretory clearance of UA, OXY and ALLO will be calculated from serum and plasma drug levels by standard pharmacokinetic methods. To assess net secretory or reabsorptive clearance of the three compounds, we will subtract $f_u \cdot \text{GFR}$ (where f_u is the unbound fraction of ALLO, OXY or UA and GFR is the glomerular filtration rate), as measured or estimated from serum and urine creatinine values, from renal clearance of ALLO, OXY and UA, directly measured from plasma and urine values. Previously we have used these methods to calculate net secretion (or reabsorption) of several drugs. For pharmacodynamics, differences in DSUA between the genotype groups will be evaluated first with an analysis of variance. If DSUA is not normally distributed, we will evaluate the differences between the genotype groups using a non-parametric Kruskal-Wallis test. We expect individuals with ABCG2 141K/K and 141Q/K will have a reduced response to ALLO (smaller DSUA) than individuals with ABCG2 141Q/Q. In addition, individuals with ABCG2 141K/K will have reduced renal clearance of ALLO and OXY in comparison to other genotypes since we propose that ABCG2 functions as a secretory

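### Tubular OXY, and the secretory clearance behind it, cannot be identified from the planned data if OXY is reabsorbed, so results should be reported conditional on a reabsorbed fraction.

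*Combined protocol and SAP*

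**What the plan says.** BACKGROUND item 4 sets out the mechanism. ABCG2 secretes OXY into the tubule, where it should "competitively inhibit uric acid reabsorptive transporters, e.g., URAT1". The same item reports that OXY is itself carried by URAT1, citing earlier work that the team's own data are said to agree with.

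STATISTICAL ANALYSIS then makes three relevant statements:

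- **Tubular model.** It uses plasma and urine OXY, and "by estimating filtration and secretory clearance of OXY, we will be able to estimate the time profile of tubular concentrations of OXY". The result is treated as the concentration at the site of action and linked, by a linear or Emax relationship, to inhibition of UA reabsorption. UA is the only compound for which reabsorption is modelled. The section allows for saturable secretion of OXY but gives OXY no reabsorption term.
- **Net clearance.** "To assess net secretory or reabsorptive clearance of the three compounds, we will subtract" fu·GFR from renal clearance, "where f_u is the unbound fraction of ALLO, OXY or UA and GFR is the glomerular filtration rate".
- **Endpoints and power.** The modelling is said to have "at least 80% power to detect differences in primary endpoints (net secretory clearance and change in UA) as described above". No compound is named for net secretory clearance.

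The end of the section also plans a genotype comparison of renal clearance itself, for ALLO and OXY.

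**The concern.** The two sections do not fit together. If URAT1 carries OXY back out of the tubule, urinary OXY is what remains after filtration, secretion and reabsorption. The plan has one observed quantity (CLr, with fu·GFR taken as known) and two unknowns (secretion and reabsorption). A model with filtration and secretion only resolves this by silently setting reabsorption to zero.

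Tubular OXY is the quantity on which the proposed mechanism rests. Its level, any EC50 estimated against it, and the absolute secretory clearance would all depend on an assumption that the plan does not state and that its own background contradicts. Secondly, a reader could take the net clearance of OXY as a measure of ABCG2 secretion, and so take a null net result as absence of an ABCG2 effect.

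**Working it through.** **The plan's own figure.** The only sample-size statement, under NUMBER OF SUBJECTS, is that with 5 subjects per genotype "our study will be 80% powered to detect a 40% change in allopurinol clearance". It gives no CV, alpha or test, so it cannot be reproduced. At two-sided alpha 0.05 it implies a CV of roughly 17% to 26%, depending on the test and the scale. It concerns allopurinol clearance and does not bear on whether tubular OXY can be identified.

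**Inputs.** From the documents: net clearance = CLr − fu·GFR; OXY carried by URAT1; URAT1 reabsorptive; 5 subjects per genotype. Not in the documents, and assumed here: the reabsorbed fraction R, the secretory clearance CLs, fu·GFR = 100 ml/min, and reabsorption acting on the combined filtered and secreted load.

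**Step 1: identification.** With first-order reabsorption,

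CLr = (fu·GFR + CLs)(1 − R).

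The tubular load per unit plasma concentration is fu·GFR + CLs = CLr/(1 − R). Take CLr = 60 and fu·GFR = 100:

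| R | Load = 60/(1 − R) | CLs = load − 100 |
|---|---|---|
| 0.4 | 100 | 0 |
| 0.6 | 150 | 50 |
| 0.8 | 300 | 200 |

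All three rows reproduce the same CLr. The load differs threefold, and so does an EC50 expressed on that scale.

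**Step 2: when the model without reabsorption fails.** Without R, CLr = fu·GFR + CLs, so CLs ≥ 0 requires CLr ≥ fu·GFR. Under Step 1, CLr falls below fu·GFR once R > CLs/(fu·GFR + CLs): 50/150 = 0.33 for CLs = 50, and 100/200 = 0.5 for CLs = 100. Beyond that point a filtration-plus-secretion model cannot fit OXY with a non-negative secretory clearance.

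**Step 3: the net clearance.** From Step 1,

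CLr − fu·GFR = (1 − R)·CLs − R·fu·GFR.

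With a common R and equal GFR, the genotype difference is (1 − R)·ΔCLs. For CLs of 50 in Q/Q and 30 in K/K (40% lower), ΔCLs = 20 and the net difference is 20, 15, 10, 4 and 2 ml/min at R = 0, 0.25, 0.5, 0.8 and 0.9.

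If reabsorption is instead saturated, removing a constant T in clearance units, CLr − fu·GFR = CLs − T. The difference is then (50 − T) − (30 − T) = 20 for any common T. There is no shrinkage, but CLs and T are still not separable from their difference.

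**Step 4: would a ratio endpoint repair it?** Simulated standardised effects (Q/Q minus K/K over the pooled SD), assuming fu = 1, GFR SD 15, CV of CLs 15%, and 10% error in CLr and in GFR:

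| R | Net, R identical in all | log[CLr/(fu·GFR)], R identical in all | Net, SD of R 0.10 | log ratio, SD of R 0.10 |
|---|---|---|---|---|
| 0 | 1.10 | 0.94 | – | – |
| 0.25 | 0.96 | 0.94 | 0.71 | 0.70 |
| 0.5 | 0.68 | 0.94 | 0.49 | 0.55 |
| 0.8 | 0.25 | 0.94 | 0.19 | 0.21 |

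The ratio is stable only when every subject has the same R. With modest variation in R most of its advantage goes. Plain log CLr gives about 0.93 at every common R, practically the same as the ratio, and a CLr comparison is already planned.

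**The case against.** The strongest case for the plan has four parts.

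- **The subtraction is right for what it is called.** CLr − fu·GFR is net clearance by definition, the text allows for a reabsorptive result, and negative values are therefore foreseen. This stands. The problem lies only in interpreting the net value as secretion or feeding it into tubular load.
- **The primary endpoint is not tied to OXY, and a CLr comparison is already planned.** This also stands. A genotype effect hidden in the net OXY difference could still show in CLr.
- **The plan hedges.** It speaks of attempting the tubular estimate and says other factors may be accounted for. But the same sentence goes on to assert that the estimate will be obtainable, and no OXY reabsorption term is named.
- **Concentration dependence over the sampling period might help identification.** In principle it could, weakly. As written, however, only secretion may saturate, so a change in reabsorption with concentration would be attributed to secretion.

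A reader might infer two stronger points. One is that reabsorption necessarily shrinks the genotype signal, so the primary comparison should become log[CLr/(fu·GFR)]. The documents do not support this: shrinkage requires first-order reabsorption, none appears when reabsorption is saturated, and BACKGROUND item 4 itself expects tubular levels possibly in the mM range, where saturation is conceivable. The other is that the direction of the OXY–UA link is arbitrary. With a common R, tubular load is only rescaled by 1/(1 − R), so the ordering of subjects is unchanged. Ordering is at risk only if R differs between subjects or with concentration.

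**Conclusion.** The concern holds for identification. Given the protocol's own statement about URAT1, the level of tubular OXY, any EC50 built on it, and the absolute secretory clearance of OXY are not identified by the planned data and model. In the worked example the load spans 100 to 300 for the same observed CLr. That range illustrates the problem and does not estimate its size in this trial, because the documents give no R, fu or secretory clearance for OXY.

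The net clearance endpoint is valid as a net quantity. Whether its genotype difference is attenuated depends on the form of reabsorption: by a factor (1 − R) if first-order, not at all if saturated. The size cannot be stated, and the case for replacing the primary comparison is not made. The gap should be corrected in the analysis text, since the tubular profile carries the mechanistic conclusion.

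**What to change.** In STATISTICAL ANALYSIS:

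1. Add an OXY reabsorption term to the tubular model. Rerun it over a range of R fixed in advance, for example 0 to 0.9, including a case in which R differs between subjects or is saturable.
2. Report tubular OXY, the EC50 and OXY secretory clearance as ranges conditional on R, and replace the assertion that the tubular profile can be estimated with that conditional statement. State which values of R are incompatible with the data (those implying negative secretion).
3. State that the net clearance of OXY combines secretion and reabsorption. Interpret it beside the planned genotype comparison of CLr, so that a null net result is not read as no ABCG2 effect.
4. Optionally add log[CLr/(fu·GFR)] as a sensitivity analysis, not as the primary.

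The cost is some wording and a few extra model runs, with no new samples or visits. The drawback is that the tubular concentration claim becomes conditional.

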The Effects of BCRP Q141K on Allopurinol Pharmacokinetics and
Dynamics

NCT02956278
Sept 2017

PURPOSE: To investigate the potential association of polymorphic genetic variants ABCG2 with altered response to allopurinol, we will employ a genotype to phenotype strategy. Specifically, we will evaluate this hypothesis in Asians and Europeans, populations with rapidly growing incidence of hyperuricemia and gout that carry these genetic variants. To assess the effects of these variants on allopurinol response, we will measure serum uric acid and renal uric acid clearance as well as serum and urinary concentrations of allopurinol and its active metabolite, oxypurinol, to determine pharmacokinetic parameters. Other analyses may be done in the calculation of these parameters, such as serum creatinine and creatinine clearance.

BACKGROUND:

1. Gout is a major medical condition with a high prevalence in the U.S. and an increasing prevalence in global populations. Gout is an inflammatory arthritic disease caused by elevated serum uric acid (UA) levels. In humans, UA is the end-product of purine metabolism, and high UA levels are associated with gout and increased risk for cardiovascular events including stroke and myocardial infarction. Historically, because of protein-rich diets, gout was termed a “rich man’s disease” and confined to Western populations. However, with the global epidemic of metabolic syndrome, the prevalence of gout in other populations has increased dramatically^{1,2}, e.g., certain populations in Asia, Polynesia and Africa have prevalence rates exceeding 10%^{3,4}.

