2. Allopurinol (ALLO) is first line therapy for gout prevention with emerging uses in other diseases associated with metabolic syndrome. Discovered in the 1940s by researchers at Burroughs Wellcome, including Nobel laureates Elion and Hitchings, ALLO has been first-line therapy for the treatment of hyperuricemia and gout for many years. ALLO is considered a pro-drug with weak pharmacologic effects; it is converted to an active metabolite, oxypurinol (OXY) via aldehyde oxidase, AOX1. OXY is a potent inhibitor of xanthine oxidase, the primary enzyme involved in the synthesis of UA. Though its major use is in the treatment of gout, ALLO is used for other diseases such as tumor lysis syndrome and kidney stones⁵⁻⁷, and is being repurposed for the treatment of diseases associated with metabolic syndrome, e.g., heart failure, stroke and cardiac shock⁸⁻¹¹. Other xanthine oxidase inhibitors are also on the market or in clinical drug development.

3. Recent data from our laboratory challenge the widely accepted mechanism of action of ALLO and OXY as its sole mechanism and suggest a major role for BCRP.

In the first GWAS of ALLO response, we observed a single locus, in ABCG2, strongly associated with response to ALLO in 1300 patients of European ancestry. Previous genomewide association studies have shown ABCG2 and other UA transporters (e.g. GLUT9, URAT1) to be associated with high UA levels¹²⁻¹⁵. However, in our population of gout patients on ALLO, only ABCG2 (and not the other UA transporters) was significantly associated with drug response, i.e., ALLO-induced changes in UA levels. These results suggest that the gene may act on OXY directly. In fact, in exciting follow-up studies in our laboratory, we found that both ALLO and OXY are excellent substrates of ABCG2 in HEK293 cells over-expressing the transporter suggesting that ABCG2 may

function directly in the pharmacokinetics of ALLO/OXY. These results are consistent with other pharmacogenomic studies that show that genetic variants in membrane transporters that affect pharmacokinetics are associated with altered drug response (e.g., SLC01B1 and methotrexate and statin toxicities, and ABCG2 and rosuvastatin response)¹⁶⁻¹⁹. Because of its location on the apical membranes of intestinal and renal epithelia, the data suggest that ABCG2 functions in reducing the intestinal absorption and enhancing the renal secretion of the drugs as it does for several other drugs²⁰⁻²².

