Phase I procedures: Subjects will be asked to come to the clinic after 8 hours of fasting to provide a 10 ml blood sample to determine baseline serum uric acid and creatinine concentrations. Female subjects will be asked to provide a urine sample (20 mL) to ensure no change in pregnancy status. Subjects will be asked to empty their bladder and will then be given a placebo (microcrystalline cellulose). Blood samples will be collected at the following time points via an IV catheter: 0.5, 1, 1.5, 2, 3, 4, 5, 6, 8, 10, 24 hours. Subjects will be asked to collect all urine samples during their stay. The volume of the urine will be recorded and 20 ml of the sample stored at -20°C for analysis of uric acid and creatinine content. The remaining urine will then be stored with all other urine samples from the subject until the last time point. Subjects will be asked to return in the morning for their 24 hour blood draw and final urine sample. Subjects will be asked to turn in any urine from overnight. 20 ml of the 24-hour collective urine sample will be stored at -20°C for analysis of uric acid and creatinine.

Phase II Procedures: Day 1: Subjects will be asked to come to the clinic after 8 hours of fasting to provide a 10 ml blood sample to determine baseline serum uric acid and creatinine concentrations. Female subjects will be asked to provide a urine sample (20 mL) to ensure no change in pregnancy status. Subjects will be asked to empty their bladders and will then be given 300 mg of allopurinol. Blood samples collected at the following time points via an IV catheter: 0.5, 1, 1.5, 2, 3, 4, 5, 6, 8, 10, 24 hours. Subjects will be asked to collect all urine samples during their stay. The volume of the urine will be recorded and 20 ml of the sample stored at -20°C for analysis of uric acid, drug, and creatinine content. The remaining urine will then be stored with all other urine samples from the subject until the last time point. Subjects will be asked to return in the morning for their 24 hour blood draw and final urine sample. Subjects will be asked to turn in any urine from overnight. 20 ml of the 24-hour collective urine sample will be stored at -20°C for analysis of uric acid, drug, and creatinine.

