| Phase 2: Allopurinol – Oral 300 mg tablet | 72 hours after first dose Day 4 – at home | Patient Diary and phone follow-ups |
| Phase 2: Allopurinol – Oral 300 mg tablet | 96 hours after first dose Day 5 – at home | Patient Diary and phone follow-ups |
| Phase 2: Allopurinol Final Oral 300 mg tablet | 120 hours after first dose Before – Fast 8 hours Day 6 – clinic visit | Blood: Baseline- Creatinine, UA, ALLO/OXY During at 0.5, 1,1.5, 2, 3, 4, 5, 6, 8, 10 hours (Creatinine, UA, ALLO/OXY) Urine: Before – females 20 ml for pregnancy test. During- all urine during stay collected |
| Phase 2: Allopurinol – Follow-up | 24 hours after final dose Day 7 – clinic visit | Blood: Creatinine, UA, ALLO/OXY Urine: Turn in urine that was collected overnight |
| Phase 2: Allopurinol – Follow-up | Day 8 – clinic visit | Blood: Creatinine, UA, ALLO/OXY |
| Phase 2: Allopurinol – Follow-up | As close as possible to 72 hours after injection Day 9 – clinic visit | Blood:, Creatinine, UA, ALLO/OXY |

ANALYTICAL METHODS: Measurement of allopurinol and oxypurinol will be performed by high performance liquid chromatography and mass spectrometry (LC-MS/MS). Measurement of uric acid and its precursors, xanthine and hypoxanthine, will be measured via Amplex Red and Abcam colorimetric assays.

Genotyping: All recruited subjects will sign informed consents and HIPAA forms. At screening, a blood sample (10 mL) or saliva sample will be obtained for DNA extraction. Plasma will be stored for assays of endogenous compounds and drugs. The ABCG2 variants will be genotyped at UCSF by a Taq Man Assay using primers and probes from ABI. The reaction will be run on an ABI 7900 HT.

HLA genotyping and wellness panels will be analyzed by qualified personnel at OMI or other reputable company as approved by [name] or other study personnel.

STATISTICAL ANALYSIS:

Mechanistic pharmacokinetic modeling will be conducted to characterize the pharmacokinetics of allopurinol (ALLO) and oxypurinol (OXY). The mechanistic model will characterize details relevant for this study such as conversion mechanism from ALLO to OXY and estimation of fraction of metabolized drug; estimation of ALLO and OXY renal and secretory clearance; possible concentration-dependent saturation

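### The PD model names a renal drug effect but no effect on urate production, its fitted outputs are unstated, and no placebo-to-allopurinol contrast of urate clearance is named

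*Combined protocol and SAP*

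**What the plan says.** **The model.** STATISTICAL ANALYSIS gives the pharmacodynamic (PD) model one drug effect: "A model describing concentration dependent inhibition of UA re-absorption from the renal tubule by OXY will be implemented". Linear and Emax forms are to be tried, both acting on reabsorption. Tubular OXY is linked to the fall in plasma UA, and the section says the modelling will strongly support the mechanistic hypothesis. It does not list which observations the model predicts and which it takes as inputs.

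**The drug's other action.** BACKGROUND item 2 states that "OXY is a potent inhibitor of xanthine oxidase, the primary enzyme involved in the synthesis of UA". Item 3 says the laboratory's data "challenge the widely accepted mechanism of action of ALLO and OXY as its sole mechanism". The production effect is thus disputed only as the whole explanation.

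**Checks already in the plan.**
- PURPOSE: "we will measure serum uric acid and renal uric acid clearance", in order to assess the variants' effect on response. STATISTICAL ANALYSIS explains how UA renal and net reabsorptive clearance are obtained from plasma and urine.
- Phase I procedures: "Subjects will be asked to empty their bladder and will then be given a placebo (microcrystalline cellulose"), followed by 24 hours of blood and urine collection, with UA and creatinine measured in the urine.
- ANALYTICAL METHODS: "Measurement of uric acid and its precursors, xanthine and hypoxanthine, will be measured via Amplex Red and Abcam colorimetric assays". No analysis of the two precursors is described.
- STATISTICAL ANALYSIS expects better responders to show higher urine UA concentrations.

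**Named comparisons.** The only PD comparison with a named test is DSUA (apparently the change in serum UA) between genotypes, by analysis of variance or Kruskal-Wallis. The genotype expectation for renal clearance names ALLO and OXY. The closing sentence on 141K carriers and renal clearance names no compound.

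**The concern.** The study's central claim is that ABCG2 alters response through the kidney: less OXY reaches the tubule, so less UA reabsorption is blocked. A model whose only drug effect is renal has nowhere else to put a fall in serum UA. If serum UA is what it predicts, it will report a renal effect even when the whole fall comes from reduced synthesis. A good fit to serum UA would then say nothing about which mechanism operates.

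The comparison that would separate the two mechanisms is whether UA renal clearance itself changes from placebo to allopurinol. The data for it are collected, but the comparison is not named. An analyst following the text could report a renal mechanism from the model without ever showing that UA clearance moved.

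**Working it through.** The plan gives no figure for UA clearance or for the PD model to reproduce. Its sample-size statement concerns allopurinol clearance, gives no CV or alpha, and does not bear on this point. All inputs below are assumptions shown as ranges, except the 15 subjects (5 per genotype), the serum sampling times and the two-phase design.

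**1. Serum UA as the predicted output (steady state).** Let *p* be the fractional serum fall, *fr* the renal share of UA loss at baseline, and *c* the on-drug/placebo ratio of UA renal clearance. Truth: production falls by *p* and clearance is unchanged (*c* = 1). A renal-only model holds production at baseline, so it needs (fr·c + 1 − fr)(1 − p) = 1, which gives

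c = 1 + (1/(1 − p) − 1)/fr.

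| Serum fall | c, fr = 1 | c, fr = 0.67 | Urine UA the model implies, c(1 − p) | True urine UA, 1 − p |
|---|---|---|---|---|
| 20% | 1.25 | 1 + 0.25/0.67 = 1.37 | 1.00; 1.10 | 0.80 |
| 30% | 1.43 | 1 + 0.429/0.67 = 1.64 | 1.00; 1.15 | 0.70 |
| 40% | 1.67 | 1 + 0.667/0.67 = 2.00 | 1.00; 1.20 | 0.60 |

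Urine UA is excretion relative to placebo; paired values are for fr = 1 and fr = 0.67.

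**2. Serum and urine fitted jointly.** Turnover model: dS/dt = k[(1 − I) − (fr·c + 1 − fr)S], with k = 0.4-0.8 per day and a constant production cut I from the first dose. It was fitted to end-of-day serum and 24-hour urine on Days 1 and 6, with squared errors on the log scale. Truth is again 1.00.

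- Serum only, 30% cut: 1.38-1.39 (fr = 1), 1.57-1.59 (fr = 0.67).
- Equal weights, 30% cut: 1.19-1.26 (fr = 1), 1.04-1.10 (fr = 0.67). Over cuts of 20-40%: about 1.1-1.4 and 1.0-1.2.
- Urine weighted ten to one, 20-40% cut: 0.90-0.97 and 0.72-0.90. The bias has reversed.

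The error shows as misfit. For the 30% cut with equal weights and fr = 1, true Day 6 excretion is 0.70-0.73 of baseline and the fitted value is 1.00-1.01.

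In a 15-subject simulation with more precise serum (CV 5%) than urine (CV 10%, plus 10-20% per subject-day, six collections a day), the joint fit stayed close to the serum-only size: 1.23-1.35 for a 20% fall and 1.65-1.97 for 40%. Day 6 urine UA lay 10-13% and 21-27% below the fitted values.

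**3. Observed serum as input, urine UA as response.** In the same simulation the renal-only model gave 0.99-1.00, so the bias is absent.

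**4. Alternatives, same simulation (5th-95th percentiles in brackets).**
- True ratio 1.00: two-effect joint model 1.00-1.02 (within 0.87-1.20); direct clearance contrast 0.99 (0.87-1.11).
- True ratio 1.25 with a 40% fall: renal-only joint fit 1.65-1.97; two-effect model 1.25-1.27 (1.17-1.40); direct contrast 1.24 (1.07-1.39).

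OXY exposures, UA volume and renal share were treated as known. Fixing the wrong renal share moved the two-effect estimate from 1.25 to 1.21-1.30.

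**5. Urine UA as a discriminator.** For a 40% serum fall, excretion relative to baseline is 1.13-1.52 on Day 1 and 1.00-1.21 on Day 6 if only reabsorption is inhibited. If only production is inhibited it is 0.79-0.95 and 0.60.

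**6. Precision of the direct contrast.** Detectable ratio = exp(d·√(2 ln(1 + CV²))), two-sided 5%, 80% power, noncentral t: d = 2.02 for 5 v 5 and 0.78 for one sample of 15. At an assumed within-subject CV of 10/15/20%, √(2 ln(1 + CV²)) = 0.141/0.211/0.280. All 15 subjects therefore detect a 1.12/1.18/1.24-fold change; 5 v 5 detects a 1.33/1.53/1.76-fold difference in change.

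**The case against.** The best defence is that the text is brief rather than wrong.

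- The model sentence describes only the tubular step, so observed serum UA could be an input and urine UA the response; that version is unbiased.
- The section speaks broadly of UA physiology and metabolism, and adding a production term is ordinary model development.
- PURPOSE ties renal UA clearance to the variants' effects, which is in intent a genotype comparison.
- The predicted rise in urine UA separates the mechanisms, since production inhibition lowers UA excretion.
- BACKGROUND item 4 reasons from direction: "The fact that we found that the variant was associated with a worse response suggests another mechanism". DSUA by genotype tests that direction.
- The primary endpoints, net secretory clearance and change in UA, do not need the PD model.

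Much of this stands. A reader might infer that the model as specified cannot support the renal mechanism. The documents do not support that: the outputs are unstated, a production term is not excluded, and one permissible version is unbiased. A reader might also infer that UA clearance goes unexamined. It does not; only the placebo-to-allopurinol contrast is missing. Nor can one say that adding urine data either cures or preserves the bias, because that turns on the weighting.

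What remains is still material. The response is described as plasma UA lowering, which makes serum UA the more natural output. The flexibility offered, "the modeling may also account for other factors contributing to high tubular concentration", concerns tubular concentration and not synthesis. A genotype difference in DSUA or UA clearance does not by itself show that the drug changed UA clearance. Urine concentration also varies with urine volume, and on Day 6 the renal mechanism alone need not raise excretion above placebo.

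**Conclusion.** The concern holds as under-specification with a possible serious consequence. The plan names no production effect, does not state the fitted outputs, and does not name the contrast that would settle the question. Whether the mechanistic claim is misled depends on those choices: overstatement is greatest when serum UA is the predicted output, variable in size and sign in a joint fit, and close to nil when serum is an input.

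The sizes rest on an assumed serum fall of 20-40% and an assumed renal share of 67-100%. The joint-fit figures rest further on assumed turnover and error weights. This should be corrected before analysis. Confidence is medium, because the intended fit may already be one of the unbiased forms.

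**What to change.** 1. Name the main mechanistic test: the within-subject placebo-to-Day 6 ratio of UA renal clearance, or of UA to creatinine clearance in the same urine. Estimate it first in all 15 subjects, then by genotype with confidence intervals, described as a low-precision estimate.
2. State the fitted outputs. Add a production-inhibition effect driven by plasma OXY beside the reabsorption effect driven by tubular OXY. Fit serum and urine UA jointly, with the placebo phase as the no-drug reference. Base the renal claim on the reabsorption term with production included, expressed as a clearance ratio and not as an EC50. Use the planned xanthine and hypoxanthine assays as a check, and confirm by simulation that both effects can be estimated.
3. Read urine UA as excretion relative to the placebo day, together with serum UA. Absence of a Day 6 rise does not refute the renal mechanism.

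The cost is SAP wording and modelling time; serum and urine UA and creatinine are already collected in both phases. The downsides are one or two more parameters and a weakly estimated EC50. In the simulations the reabsorption EC50 reached its search limit in 48-71% of trials with no renal effect, and in 0-8% when the true ratio was 1.25 with a 40% fall. The direct contrast needs no EC50, but its genotype comparison can detect only large differences.
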